##### 4.8.1 Primary Endpoint [IRCRSLT] (population for the primary analysis and PEP)

The primary endpoint is defined as the percentage of subjects shedding virus by PCR in nasopharyngeal swabs obtained at Day 3.

- a. Completeness of viral shedding results showing number (%) at Day 0, 3 and 7 who:
  - had qPCR result
  - were lost to follow-up prior to the visit
  - were in follow-up but had missing value
- b. Primary Analysis: Among subjects with Day 3 qPCR results, number (%) with detectable viral shedding at Day 3. Comparison of randomized arms with associated 95% confidence interval and p-value based on the normal approximation to the binomial distribution.

- c. Sensitivity Analyses (PEP only): to assess potential impact of missing measurements. Repeat the primary analysis (above) considering missing measurements in turn as (a) above the limit of detection, or (b) below the limit of detection, or (c) above the limit of detection in one randomized arm and below in the other arm (so as to maximize the difference between arms), or (d) the opposite of (c) (so as to minimize the difference between arms).
- d. Sensitivity Analyses (PEP only): Repeat the primary analysis above but restricted (a) to samples in which one or more housekeeping genes had detectable levels (hence indicating adequate sample); and (b) to samples in which all housekeeping genes had detectable levels.
- e. Subgroup Analyses (PEP only): Comparison of randomized treatments will be undertaken by sex (male vs female), influenza type (A vs B), and country/race (US/white vs US/non-white vs Thailand vs other countries). To assess whether the difference between randomized treatments varies by subgroup, a treatment by subgroup interaction test will be undertaken using logistic regression.

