5.1 Method of Assignment to Treatment

Subjects who meet all criteria for enrollment will be randomized using an interactive web-based system. A central randomization scheme will be prepared by the sponsor or designee.

Additionally randomization will be stratified based on duration of symptoms prior to randomization: (0–24 hours and 25–48 hours).

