9.2.1 Sample Size Re-estimation

After analysis of the pilot study data, the primary endpoint was chosen as the percentage of subjects shedding virus by PCR in NP swab at Day 3.

Assumptions:

- Pooled percentage of subjects with virus detectable by PCR at Day 3 combining both arms is 50% (based on pilot study data)
- Require 90% power to detect difference between arms using two-sided Fisher’s Exact Test with Type I error rate of 0.05.
- Proportion of participants with missing qPCR at Day 3 is 10% (due to losses to follow-up, sample handling and laboratory assay problems).

| Magnitude of difference in proportions between arms (proportions in the two randomized arms) | Sample size (combined across both arms) without adjustment for missing values | Sample size (combined across both arms) with adjustment for 10% with missing values & not accounting for the 50 subjects in the pilot study) |
|--|---|--|
| 25% (37.5% vs 62.5%) | 174 | 194 |
| 20% (40% vs 60%) | 280 | 312 |
| 15% (42.5% vs 57.5%) | 490 | 546 |

Table 9: Re-estimated Sample Size Under Different Treatment Effects

This sample size has been chosen to give approximately 90% power to detect an absolute difference of 15% in the proportion of subjects with undetectable virus shedding at Day 3 in NP swabs (e.g., a reduction of 15% from 57.5% in the oseltamivir arm to 42.5% in the placebo

arm). Less than a 15% absolute difference in viral shedding is unlikely to be viewed as clinically meaningful. Therefore, the revised sample size calculations confirm keeping the sample size 560 subjects, including 50 in the pilot study and 510 in the main study.

This power calculation is based on the fact that approximately 50% of subjects in the pilot study had undetectable virus in NP swabs at Day 3 (pooled over randomized arms) and included allowance for 10% of subjects to have unavailable viral shedding results at Day 3. The calculation assumed use of a t-test to compare proportions using a two-sided type I error rate of 0.05.

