##### 4.1 Analysis Populations

All tables and figures will note the analysis population used:

- Enrolled Population includes all subjects who had a signed informed consent form for screening.
- Intention To Treat (ITT) Population includes all subjects who were randomized and who received at least one dose of study drug (as defined in Section 7.2.1 of the protocol).
- Primary Efficacy Population (PEP) includes subjects in the ITT population with influenza infection confirmed in central laboratory testing. Given the virology needed to analyze the primary endpoint, this is defined as having an influenza virus isolated and typed in the qualitative PCR evaluation at Day 0 from central laboratory testing (or Day -1 if Day 0 not available).
- The population for the primary analysis is defined as the subgroup of the PE Population that excludes the subjects who participated in the pilot study (because efficacy results for those subjects were used in selecting the primary endpoint for the study).

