#### 4.3.4 Virology Measures (ITT and PEP) [team collected swabs]

- a. Viral shedding in nasopharyngeal (NP) swab by qPCR: number (%) <LOD, LOD-<LLOQ, ≥LLOQ, and summary of quantitative values on log10 scale [IRCRSLTS]
- b. Housekeeping (HK) gene levels by qPCR: number (%) <LOD, LOD-<LLOQ, ≥LLOQ-≤ULOQ, >ULOQ, and summary of quantitative values on log10 scale [IRCRSLTS]
- c. Viral shedding in nasopharyngeal (NP) swab by qPCR by housekeeping gene detection [IRCRSLTS]:

- NP virus <LOD: % HK <LOD, % HK LOD-<LLOQ, % HK  $\geq$ LLOQ- $\leq$ ULOQ, % HK >ULOQ
- NP virus LOD-<LLOQ: % HK <LOD, % HK LOD-<LLOQ, % HK  $\geq$ LLOQ- $\leq$ ULOQ, % HK >ULOQ
- NP virus  $\geq$ LLOQ: % HK <LOD, % HK LOD-<LLOQ, % HK  $\geq$ LLOQ- $\leq$ ULOQ, % HK >ULOQ

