#### **4.8.2 Secondary Endpoints: Virologic Endpoints [IRCRSLTS] (PEP and ITT)**

Viral shedding will be assessed by quantitative RT-PCR (reported as  $\log_{10}$  RNA copies/mL) with measurements obtained on Days 0, 3, and 7. These measurements will be used to define the following variables:

- a. Figure and associated table showing number (%) of subjects who had values  $<LOD$ ,  $LOD-<LLOQ$ ,  $\geq LLOQ$  at each visit.
- b. Figure and associated table showing number of subjects and minimum, maximum, median, 25% and 75% percentile of the value of viral shedding at each visit (subjects with values  $<LOD$  will be ranked as lower than detectable values in this analysis; minimum and maximum in table only). Comparison of randomized arms at each of Day 3 and Day 7 will be based on the extension of Wilcoxon's test to handle censoring of measurements which are  $<LLOQ$ .
- c. Number (%) of subjects with undetectable viral load at both Day 3 and Day 7; detectable at Day 3 and undetectable at Day 7; detectable at Day 7 (irrespective of whether or not detectable at Day 3). Analysis will be restricted to subjects with measurements at both Day 3 and Day 7. Comparison of percentages of subjects in this table using the Wilcoxon Test.
- d. Above tables/figures/analyses will be repeated for the subset of subjects who had detectable viral load at Day 0.

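### The primary Day 3 comparison uses neither the randomisation stratum nor the Day 0 viral load; adjusting for both could tighten the estimate at no cost in patients

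*SAP*

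**What the plan says.** **Primary analysis.** SAP 4.8.1b, among subjects with a Day 3 qPCR result: "Comparison of randomized arms with associated 95% confidence interval and p-value based on the normal approximation to the binomial distribution". Items c and d repeat that comparison under different handling of missing or inadequate samples. The only regression for this endpoint is in item e, a logistic model for subgroup interactions by sex, influenza type and country/race.

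**Stratum.** Protocol 5.1 states that "randomization will be stratified based on duration of symptoms prior to randomization", with strata of 0–24 and 25–48 hours. No planned analysis of the primary endpoint uses it.

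**Day 0 viral load.** SAP 4.8.2 describes quantitative RT-PCR on the log10 scale "with measurements obtained on Days 0, 3, and 7", and SAP 4.3.4a summarises the Day 0 values. For central confirmation of influenza, SAP 4.1 says "this is defined as having an influenza virus isolated and typed in the qualitative PCR evaluation at Day 0 from central laboratory testing", with Day -1 allowed as a fallback. Every subject in the primary analysis therefore has a baseline central sample.

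**Precedent in the SAP.** Section 4.10g stratifies the self-swab AUC test by quartile of the Day 0 measurement.

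**Sizing.** Protocol 9.2.1: "This sample size has been chosen to give approximately 90% power to detect an absolute difference of 15% in the proportion of subjects". It names Fisher's exact test in the assumptions and then says "The calculation assumed use of a t-test to compare proportions using a two-sided type I error rate of 0.05". Both are unadjusted.

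**The concern.** Viral load at entry is a natural candidate predictor of whether virus is still detectable three days later. If it does predict this, the crude comparison leaves that variation in the standard error, and the interval on the one powered endpoint is wider than it need be. The stratum matters for a second reason: the usual advice is that the analysis should reflect the way subjects were randomised.

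The plan has little to spare. The 10% allowance in Protocol 9.2.1 covers missing Day 3 qPCR only. It does not cover subjects randomised on a site test who then fail central confirmation and leave the Primary Efficacy Population. Precision that costs no patients is worth having here.

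**Working it through.** **Inputs (Protocol 9.2.1 unless stated):** 42.5% v 57.5%; two-sided 0.05; 90% power; 10% missing; 510 main-study subjects, pilot excluded; 1:1 allocation (Protocol 3.1). The prognostic strength of Day 0 load and of the stratum is not given and is assumed below.

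**1. The plan's own figure.** The pooled normal formula gives, per arm,

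(1.960·√(2·0.5·0.5) + 1.282·√(2·0.425·0.575))² / 0.15² ≈ 231.4, so 232 per arm or 464 in total.

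With the continuity correction this becomes 245 per arm, or 490, which matches Table 9. Exact Fisher power at 245 per arm is 90.3%. 490/0.90 = 544.4, so 545, or 546 as an even total, which also matches.

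**2. Crude analysis at the planned size.** Evaluable: 510 × 0.90 = 459.

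- Variance of the difference: 4 × 0.425 × 0.575 / 459 = 0.9775/459, so SE = 0.0461.
- Half-width: 1.96 × 0.0461 = 9.0 points.
- Power, unpooled: Φ(0.15/0.0461 − 1.96) = 90.2%.
- The pooled z-test gives 89.8% and Fisher 88.8%.
- Evaluable number for 90%, unpooled: 0.9775 × (1.960 + 1.282)² / 0.15² = 456.5, so 457. Pooled: 464.

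**3. Adjusted analysis.** To a good approximation the variance is multiplied by (1 − R²), where R² is the share of outcome variance explained by the covariates. At 459 evaluable:

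| Assumed R² | Half-width (points) | Power |
|---|---|---|
| 0 | 9.0 | 90.2% |
| 0.05 | 8.8 | 91.5% |
| 0.10 | 8.6 | 92.9% |
| 0.20 | 8.1 | 95.3% |
| 0.30 | 7.6 | 97.3% |

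**4. Simulation of the proposed estimator.** 5,000 replicates per row; n = 459; two equal strata with blocks of 4; stratum odds ratio 1.5; marginal rates held at 42.5% and 57.5%; standardised risk difference with influence-function SE.

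| OR per SD of Day 0 load | Crude power, simulated | Adjusted power, simulated | Adjusted power, formula | Adjusted half-width | Variance reduction |
|---|---|---|---|---|---|
| 1.0 | 90.1% | 90.3% | 90.4% | 9.00 | 0.6% |
| 1.5 | 89.6% | 90.5% | 91.4% | 8.84 | 4.2% |
| 2.0 | 89.0% | 92.2% | 93.0% | 8.57 | 9.9% |
| 3.0 | 89.6% | 94.9% | 95.3% | 8.10 | 19.5% |

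A variance reduction of about 20% is worth 459/0.80 ≈ 573 evaluable subjects under the crude test.

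**5. Stratum alone.** It adds about 0.1, 0.5 and 1.0 power points at stratum odds ratios of 1.5, 2.0 and 2.7. The gain comes from Day 0 load.

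**6. Type I error (50% in both arms).** Adjusted 4.9–5.4% against crude 4.7–5.2% in these runs (Monte Carlo SE 0.3). Separate runs of 10,000 to 12,000 replicates put the adjusted test between 4.8% and 5.7% (SE 0.2). Runs of 3,000 reached 6.2% in one setting (SE about 0.4). With a degrees-of-freedom correction to the SE and 10,000 replicates, the adjusted rate was 4.9–5.3% and the crude rate 4.6–5.0%.

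**7. Values below LLOQ.** The documents do not give their frequency at Day 0. With the lowest 25% set to the threshold, adjusted power in the four rows is 90.4%, 90.8%, 91.9% and 94.6%, a change of at most 0.3 points.

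**The case against.** The strongest reply is that nothing is broken. The trial was sized on an unadjusted comparison and is analysed by one. A crude risk difference is transparent and needs no model. That is true, and it is why the crude result should stay in the report.

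The benefit also rests on assumed prognostic strengths. At an odds ratio of 1.5 per SD the gain is only about 1 power point and 0.2 points of half-width. Restricting the population to Day 0 positives could narrow the spread of Day 0 load, and the simulations fit the same model that generated the data, which favours adjustment. All of this stands as a caution about size. It does not reverse the advice: in a randomised trial the standardised estimator still targets the marginal risk difference if the model is wrong, and power did not fall when the covariate was useless.

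The slight excess in type I error in some runs is fair to raise. It is small, and the degrees-of-freedom correction brings the rate to nominal.

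The 457 threshold is not a sharp line, because the SAP does not say whether the test is pooled; the pooled version needs 464. Likewise, 459 is an upper bound if some subjects fail central confirmation. If a further 5% or 10% were lost that way (an assumption), 436 or 413 would remain and crude power would be 88.6% or 86.9%. Both points make the reserve thinner.

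SAP 4.10b repeats the crude comparison in self-collected swabs so that it can be set beside the primary endpoint. The retained crude analysis keeps that possible.

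**Conclusion.** The concern holds. Neither the stratum nor Day 0 viral load enters any analysis of the primary endpoint, although both are available before treatment. This is a missed efficiency: the planned test is valid and has about 90% power on the plan's assumptions.

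At 459 evaluable and a true difference of 15 points, adjustment would raise power from about 90% to about 91%, 92–93% or 95%, for assumed odds ratios of 1.5, 2.0 or 3.0 per SD of Day 0 load. The half-width would fall from 9.0 to between 8.8 and 8.1 points. With no prognostic value, both stay where they are. Nearly all the gain depends on Day 0 load; the stratum belongs in the model mainly so that the analysis matches the randomisation. Confidence in the size is medium, because the documents give no association between Day 0 load and Day 3 detection.

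**What to change.** Before unblinding, replace the method in SAP 4.8.1b with wording such as:

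> Primary analysis: standardised (marginal) risk difference with robust 95% CI and p-value from a logistic model with arm, symptom-duration stratum as randomised, and Day 0 log10 NP viral load. Day 0 values below LLOQ, including below LOD, are set to LLOQ; a missing Day 0 quantitative value is set to the mean pooled over arms. The unadjusted comparison of proportions is supportive.

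Items c and d, which repeat the primary analysis, then use the same model. Two short additions would close loose ends: state a degrees-of-freedom correction for the robust SE, and say which Day 0 value is used for pilot subjects, who had duplicate samples and are included in items c and d. The estimator should be named explicitly, because a conditional odds ratio from the same model would be a different estimand and need not have a narrower interval.

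The cost is SAP wording, the substitution rule and slightly more analysis work. No new data or patients are needed, and no subject is dropped for a missing covariate. The headline result becomes model-based, which is why the crude comparison stays beside it. If 10% or 25% of Day 0 values fall below LLOQ, the substitution changes power by at most 0.3 points and lowers the variance reduction by at most 1.1 percentage points.

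### The missing-data and sample-adequacy checks on the primary endpoint are assigned to the PEP, which includes the pilot subjects, and not to the population of the primary analysis

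*SAP*

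**What the plan says.** SAP 4.1 defines two nested sets. The PEP is the ITT subjects with influenza confirmed by the central laboratory at Day 0; nothing in that definition removes pilot subjects. The second set does remove them: "The population for the primary analysis is defined as the subgroup of the PE Population that excludes the subjects who participated in the pilot study".

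SAP 4.8 states that the primary analysis of the primary endpoint leaves out the 50 pilot subjects and that a secondary analysis puts them back. The heading of SAP 4.8.1 names both sets. Item b is complete-case: "Among subjects with Day 3 qPCR results, number (%) with detectable viral shedding at Day 3". Item c is headed "Sensitivity Analyses (PEP only): to assess potential impact of missing measurements" and repeats item b under four scenarios for the missing swabs: (a) all detectable, (b) all undetectable, (c) split by arm to maximise the difference, (d) split by arm to minimise it. Item d repeats item b in samples with detectable housekeeping genes, and is also restricted to the PEP. The SAP gives no other missing-data analysis for this endpoint and no rule for interpreting scenarios (a) to (d).

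Protocol 9.5 gives the reason for excluding the pilot: to leave the type I error rate unaffected, since post-randomisation endpoints in those subjects were examined by arm before the endpoint was chosen. Protocol 9.1 leaves the handling of missing data to the SAP.

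**The concern.** A sensitivity analysis should change one assumption of the analysis that it tests. Set beside the primary result, items c and d as labelled change two: the handling of missing or poor samples, and the population. They also bring back the subjects whose exclusion protects the confirmatory test.

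The primary analysis drops subjects without a Day 3 result, and Protocol 9.2.1 plans for 10% of them. Missingness could be related to outcome: under Protocol 4.8, for example, a subject hospitalised within 5 days of enrolment may be withdrawn. A robustness check on the confirmatory estimate is therefore worth having, and at present it belongs to a different analysis set.

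**Working it through.** **1. Which set each analysis uses**

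| Analysis | Set named in the SAP | Pilot subjects |
|---|---|---|
| Primary, complete-case (4.8, 4.8.1b) | Population for the primary analysis | Out |
| Secondary, complete-case (4.8, 4.8.1 heading) | PEP | In |
| Missing-swab scenarios (4.8.1c) | PEP only | In |
| Housekeeping-gene restriction (4.8.1d) | PEP only | In |
| Self-swab repeat (4.10b) | Population for the primary analysis, glossed there as the PEP without the pilot | Out |

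Section 4.10b shows that the authors name the pilot-free set when they want it.

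**2. Reproducing the planned sample size**

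Protocol 9.2.1 gives the planning condition: "Require 90% power to detect difference between arms using two-sided Fisher’s Exact Test with Type I error rate of 0.05". Its 15-point row has detectable rates of 42.5% and 57.5%.

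- Uncorrected n per arm = [1.960·√(2·0.5·0.5) + 1.282·√(0.425·0.575 + 0.575·0.425)]² / 0.15² = 231.4.
- With continuity correction: (231.4/4)·[1 + √(1 + 4/(231.4·0.15))]² = 244.6, so 245 per arm and 490 in total, as stated.
- Allowing for 10% missing: 245/0.9 = 272.2, so 273 per arm and 546 in total, as stated.

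**3. Inputs for item c**

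- Protocol 9.2.1: 42.5% detectable on oseltamivir, 57.5% on placebo, 10% missing, and 560 subjects, "including 50 in the pilot study and 510 in the main study".
- 1:1 allocation gives 255 per arm without the pilot (510) and 280 with it (560).
- Assumptions: equal missingness in the two arms, and every randomised subject in the PEP. The pilot is then at most 50/560 = 8.9% of the PEP.

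With missing fraction m, an arm with observed rate p becomes (1−m)p + m if its missing results are set to detectable, and (1−m)p if they are set to undetectable. The test is the normal approximation, z = d / √[p₁(1−p₁)/n + p₂(1−p₂)/n].

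**4. Results at m = 10%**

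| Scenario in item c | Oseltamivir | Placebo | Difference | p, 255 per arm | p, 280 per arm |
|---|---|---|---|---|---|
| (a) all detectable | 48.25% | 61.75% | 13.5 | 0.002 | 0.001 |
| (b) all undetectable | 38.25% | 51.75% | 13.5 | 0.002 | 0.001 |
| (c) maximising | 38.25% | 61.75% | 23.5 | <0.001 | <0.001 |
| (d) minimising | 48.25% | 51.75% | 3.5 | 0.43 | 0.41 |

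For (d), the standard error at 255 per arm is 0.0443, so z = 0.035/0.0443 = 0.79 and the 95% CI is −5.2 to 12.2 points. At 280 per arm, z = 0.83 and the CI is −4.8 to 11.8. Including the pilot changes no conclusion in the table.

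**5. How scenario (d) depends on missingness**

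At an observed 15 points, (d) stays significant until missingness reaches about 5.6% per arm (N=510) or 5.9% (N=560). At 5% missing and N=510 it gives 9.25 points, p=0.036. At 10% missing it has about a 12% chance of significance if the planned effect is true.

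No such calculation is possible for item d, because the documents do not say what share of samples would fail the housekeeping-gene criterion.

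**The case against.** The best counter-reading is that item c says to repeat the primary analysis, so its population carries over and the PEP label means only that the ITT population is not used. This is possible, but it fits poorly with the 4.8.1 heading, which lists the two sets separately, and with 4.10b. If it is what the authors meant, the text still needs the correction.

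The second defence is that SAP 4.8 already plans a complete-case analysis in the PEP. Item c against that analysis changes only the missing-data handling, and that analysis against the primary result changes only the pilot. This stands: a reader can separate the two changes, and at least 510 of 560 subjects (91%), on the assumptions above, are common to both sets. Item a, the completeness table, carries no PEP restriction either. What remains is that the imputation and sample-adequacy checks attach to a secondary analysis.

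Three stronger readings may tempt a reader, and the documents do not support them.

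- *Scenario (d) shows that the plan is not robust.* Losing significance is normal for a worst-case bound. The SAP sets no pass/fail rule for it, and it can be significant, as step 5 shows. Scenarios (a) and (b) remain significant at the planned effect.
- *Adding the pilot could carry item c across 0.05.* An observed 9-point complete-case difference at a pooled rate of 50% does move from p=0.054 (230 per arm) to p=0.043 (252 per arm), by a pooled test. That describes the secondary analysis already planned in SAP 4.8, with no imputation. Under item c at 9 points and 10% missing, (a) and (b) give 8.1 points (p=0.065 without the pilot, 0.053 with it), (c) gives 18.1 points (p<0.001 in both), and (d) gives −1.9 points (p=0.67 and 0.65). None of the four crosses 0.05. Item d could behave like the complete-case example only if few samples were excluded.
- *The SAP lacks a missing-data analysis.* It has four scenarios; they are assigned to the wider set.

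**Conclusion.** The point holds as a mismatch of population. As written, items c and d of SAP 4.8.1 test the complete-case result with up to 50 pilot subjects included, and the confirmatory result has no imputation or sample-adequacy check in its own population. The primary estimate and its test are unaffected.

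The likely numerical consequence for item c is small: at the planned effect and 10% missing, p for the minimising scenario is 0.43 without the pilot and 0.41 with it. These figures rest on equal missingness by arm, on pilot subjects showing the same rates as the others, and on every randomised subject being in the PEP. Only centrally confirmed subjects enter the PEP, so the real numbers will be lower; with 400 subjects, for instance, scenario (d) at the planned effect gives p=0.48. The consequence for item d cannot be sized from the documents.

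**What to change.** In SAP 4.8.1 items c and d, replace the PEP-only label with: *population for the primary analysis, repeated in the PEP as supportive*. This needs no new data; the cost is a wording change and a second run of the same tables.

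Optionally, add a tipping-point table that varies the detectable percentage among missing results separately by arm and reports where significance is lost, keeping scenarios (a) to (d) as outer bounds. It would fill the gap between the equal-imputation scenarios (13.5 points at the planned effect) and the opposite-arm extremes (3.5 and 23.5 points), at the cost of one extra table. Nothing in the documents requires it, and the population correction does not depend on it.
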